8.5.10. EOS (Day 7 to 10, variable)

• Perform a limited physical examination, focusing on extremities, abdominal region, and neurological system

- Assess vital signs: HR, MAP, BP, RR, and body temperature
- Record concomitant medications and procedures
- Assess AEs and SAEs

8.5.11. Day 28 Follow-up

- Record concomitant medications and procedures administered between EOS and Day 28
- Assess SAEs via phone call to the patient's parent(s) or legal guardian(s), the patient's primary care physician, and/or a chart review

9. STUDY DRUG MATERIALS AND MANAGEMENT

9.1. Study Drug

LJPC-501 is an aqueous solution for IV infusion supplied in single-dose clear glass vials containing 2.5 mg/mL of angiotensin II and 25 mg/mL mannitol as an excipient. LJPC-501 is to be diluted in normal saline (0.9% sodium chloride solution) prior to infusion. Please refer to the Pharmacy Manual for detailed instructions.

9.2. Study Drug Packaging and Labeling

Single-dose vials of LJPC-501 will be provided that are labeled for investigational use only, in accordance with governing regulations.

9.3. Study Drug Storage.

Vials should be stored at 2-8°C in a secure area with limited access.

9.4. Study Drug Preparation

A pharmacist or designee will remove the appropriate number of vials of LJPC-501 from the refrigerator and prepare the LJPC-501 under aseptic conditions. The amount of LJPC-501 to be administered will be determined based on the Screening body weight (measurement method by local SOC). Contents of single-dose vials of LJPC-501 will be added to normal saline (0.9% sodium chloride solution). Polyvinyl chloride (PVC) or non-PVC bags are acceptable. The solution should be clear and colorless with no visible particles. Please refer to the Pharmacy Manual for detailed instructions.

Discard prepared diluted solution of LJPC-501 after 24 hours at room temperature or under refrigeration.

9.5. Administration

LJPC-501 must be delivered as an IV infusion via a central venous line.

For dosing precision, a minimum flow rate of 2 mL/hour should be used. Normal saline should be used as the carrier fluid to accomplish this minimum flow rate.

9.6. Study Drug Accountability

All used (empty and partially empty) and unused LJPC-501 vials must be saved for reconciliation by the Study Monitor or Clinical Research Associate (CRA). Following final reconciliation, all used and unused vials of LJPC-501 are to be returned to La Jolla or its designee for destruction, or destroyed (if approved by La Jolla) at the site.

9.7. Study Drug Handling and Disposal

All material containing LJPC-501 will be treated and disposed of in accordance with governing regulations.

10. ASSESSMENT OF EFFICACY

10.1. Vital Signs

Patients will be monitored for hemodynamic vital signs (MAP, HR) at Screening, at baseline, and throughout LJPC-501 administration. The Screening MAP is defined as the average of at least 2 once-hourly MAP measurements collected during SOC vasopressor titration (when total sum NED is > 0.1 μ g/kg/min), and within 24 hours prior to LJPC-501 treatment initiation. Baseline MAP is defined as the average of 3 recorded MAP values documented within 15 minutes prior to initiation of LJPC-501 (ie, approximately -15 minutes, -5 minutes, and 0 minutes or just prior to initiation of LJPC-501).

Patients will be continuously monitored during the first 24 hours following initiation of LJPC-501. Heart rate and MAP should be measured approximately once every 5 minutes during the first 15 minutes of treatment, then once approximately every 15 minutes through Hour 2 and at least once hourly thereafter through the duration of LJPC-501 administration (target minimum of 24 hours). Additionally, HR and MAP should be measured just prior to every dose titration. If LJPC-501 administration is continued for longer than 24 hours, HR and MAP should be measured hourly and just prior to any dose adjustment until LJPC-501 is discontinued.

10.2. Serum Lactate

Serum lactate (arterial or venous) measurements will be taken at baseline, at Hour 2, and at Hour 24 after LJPC-501 administration. Any other serum lactate measurements taken during the study period at the Investigator's discretion will be recorded in the electronic case report form (eCRF).

10.3. Arterial Blood Gas

ABG samples will be collected at Screening (within 6 hours prior to LJPC-501 administration) and at Hour 24.

10.4. PELOD/PRISM/PIM2 Scoring

Risk scoring indices will include the PELOD, PRISM, and PIM2 scores (Table 6).

All components of the PELOD, PRISM, and PIM2 scores will be collected during Screening, employing data obtained no more than 6 hours prior to initiation of LJPC-501 dosing. In addition, all components of PELOD, PRISM, and PIM2 scores will be collected at Hour 24 after the initiation of LJPC-501. The PELOD score is the sum of the 6 individual item scores (Appendix C). The PRISM score is the sum of the 14 individual item scores (Appendix D). The PIM2 score is the sum of the 10 individual item scores (Appendix E).

PELOD	PRISM	PIM2	
	Common to All		
Systolic BP	Systolic BP	Systolic BP	
Pupillary reactions	Pupillary reactions	Pupillary reactions	
PaO ₂ /FiO ₂	PaO ₂ /FiO ₂	$FiO_2 \times 100/PaO_2$	
	Common to 2 Scores		
Heart rate	Heart rate		
PTT or INR	PT/PTT		
Glasgow score	Glasgow score		
PaCO ₂	PaCO ₂		
Mechanical ventilation		Mechanical ventilation during first hour in ICU	
	Unique		
AST/SGOT	Bicarbonate (mEq/L)	Base excess (mmol/L) in arterial or capillary blood	
Creatinine	Total bilirubin	High risk diagnosis score	
Platelets	Calcium	Low risk diagnosis score	
WBC	Potassium	Elective admission	
	Glucose	Recovery post procedure	
	Diastolic BP	Cardiac bypass	
	Respiratory rate		

Table 6: Assessments Included in Each Pediatric Mortality Risk Score

Abbreviations: AST=aspartate transaminase; BP=blood pressure; FiO₂=fractional inspired oxygen; ICU=intensive care unit; INR=international normalized ratio; mEq=milliequivalent; PaO₂=arterial oxygen partial pressure; PaCO₂=carbon dioxide partial pressure; PELOD=Pediatric Logistic Organ Dysfunction; PIM2=Pediatric Index of Mortality 2; PRISM=Pediatric Risk of Mortality; PT=prothrombin time; PTT=partial thromboplastin time; SGOT= serum glutamic-oxaloacetic transaminase; WBC=white blood cells.

Assessments for PELOD, PRISM, and PIM2 scores are drawn from multiple sources, and Investigators should ensure all assessments are performed within the time windows for Screening (within 6 hours prior to LJPC-501 administration) and Hour 24 (± 1 hour).

- Vital signs: systolic BP, diastolic BP, HR, RR
- Hematology and serum chemistry: PTT, INR, AST, creatinine, platelets, WBC, total bilirubin, calcium, potassium, glucose
- ABG: PaO₂/FiO₂, PaCO₂, bicarbonate, base excess
- Physician assessed: pupillary reactions, Glasgow Coma Score (Appendix F), mechanical ventilation, diagnosis ratings for PIM2 (high risk diagnosis score, low risk diagnosis score, elective admission, recovery post procedure, cardiac bypass [Appendix E]).

Scores should be calculated with the most recent values prior to the assessment time point. Missing values will be assigned the last observation carried forward if missing for reason other than death or treatment failure. Missing values at Hour 24, due to death or treatment failure, will be assigned the worst possible score.

The Glasgow Coma Score (Appendix F) should be completed during a sedation holiday, if possible. If not, then the most recent non-sedated value should be used.

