6. INVESTIGATIONAL PLAN

6.1. Study Rationale

Severe hypotension is associated with significant mortality, and the use of high doses of catecholamines in patients with severe hypotension is associated with poor outcomes. Given that LJPC-501 has recently been demonstrated to be efficacious and well-tolerated in adults with hypotension who do not respond to fluids and vasopressor therapy (Section 4.5), it is reasonable to hypothesize that LJPC-501 may also be efficacious and well-tolerated in pediatric patients with the same diagnosis.

This is an open-label, multi-center study. Pediatric patients, age 2 to 17 years, who remain hypotensive despite receiving fluid therapy and vasopressor therapy and are hospitalized in an ICU setting may be eligible to participate. Because severe hypotension is life threatening, and because the treatment options are limited for pediatric patients who remain hypotensive despite fluids and vasopressors, this study will examine a single LJPC-501 treatment arm, without a placebo-controlled arm. Efficacy of LJPC-501 will be measured by each patient's response over time. To assess multiple possible improved outcomes, the primary endpoint is a composite of the proportion of patients with an increase of 25% over Baseline MAP at Hour 2 after the initiation of LJPC-501, or with a 25% reduction in sum NED at Hour 2 after the initiation of LJPC-501.

Secondary endpoints will include the change in MAP at Hour 24, and the change in serum lactate concentrations. The risk of mortality will be assessed using the PELOD score at Hour 24. Safety and tolerability will be assessed throughout the study.

Exploratory endpoints will include tissue oxygen levels, HR, reduction in sum NED at Hour 24, all-cause mortality at 28 days, the number of days that patients spend on mechanical ventilation, and the number of days on vasopressors. Exploratory measures of the risk of mortality will include PRISM and PIM2 scores at Hour 24.

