8.2. Concomitant Medications and Procedures

All patients should be given maximal supportive therapy during the course of the study. All medications and supportive therapies (including renal replacement therapy and ventilation support) that are administered from Screening through the Day 28 follow-up, including the dose and indication, must be recorded on the appropriate CRF and in the source documents. Supportive therapy that is ongoing at baseline will be permitted during the treatment phase of the study. No other experimental therapy is permitted. Concomitant medications for other medical conditions are permitted as clinically indicated. Concomitant procedures, such as dialysis, mechanical ventilation, and relevant procedures used to diagnose or treat a serious adverse event (SAE), will also be recorded from screening through Day 28.

Start and stop date(s)/time(s), dose, and amount administered will be recorded for vasopressors administered up to 48 hours prior to, during, and after LJPC-501 administration. Total daily dose for each vasopressor administered through Day 28 may be recorded after completion of LJPC-501 administration.

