APPENDIX C. PELOD SCORING

	Points assigned			
Organ system and variable	0	1	10	20
Neurologic*				
Glasgow coma score	12–15 and	7–11	4–6 or	3
Pupillary reaction	Both reactive		Both fixed	
Cardiovascular				
Heart rate, beats/min				
< 12 years	≤ 195		> 195	
\geq 12 years	≤ 150		> 150	
	and		or	
Systolic blood pressure, mm Hg				
< 1 mo	> 65		35–65	< 35
≥ 1 mo-< 1 yr	> 75		35–75	< 35 < 45
\geq 1 yr-< 12 yr	> 85 > 95		45-85	< 45 < 55
≥ 12 yr	2 95		55–95	< 22
Renal				
Creatinine, μmol/L (mg/dL)				
< 7 d	< 140 (< 1.59)		≥ 140 (≥ 1.59)	
≥ 7 d–< 1 yr	< 55 (< 0.62)		≥ 55 (≥ 0.62)	
≥ 1 yr–< 12 yr	< 100 (< 1.13)		≥ 100 (≥ 1.13)	
≥ 12 yr	< 140 (< 1.59)		≥ 140 (≥ 1.59)	
Respiratory				
PaO ₂ :FiO ₂ ratio, mm Hg	> 70		≤ 70	
	and		or	
PaCO₂, mm Hg (kPa)	≤ 90 (≤ 11.7)		> 90 (> 11.7)	
	and			
Mechanical ventilation [†]	No ventilation	Ventilation		
Hematologic				
Leukocyte count, × 10º/L	≥ 4.5	1.5-4.4	< 1.5	
	and	or		
Platelet count, $ imes$ 10 $^{\circ}$ /L	≥ 35	< 35		
Hepatic				
Glutamic oxaloacetic transaminase, IU/L		≥ 950		
Prothrombin time, % of standard (international normalized ratio)	and > 60 (< 1.40)	or ≤ 60 (≥ 1.40)		

Source: Leteurtre 2003

Abbreviations: PaO₂ arterial oxygen partial pressure; FiO₂=fractional inspired oxygen; PaCO₂=carbon dioxide partial pressure.

Note: For the Glasgow coma score, use the most recent, non-sedated value. For pupillary reactions, nonreactive pupils must be > 3 mm; do not assess after iatrogenic pupillary dilation. The use of mask ventilation is not considered to be mechanical ventilation.

Parameter	Infants	Children	All ages	Score
Systolic Blood Pressure (mmHg)	130-160	150-200		2
	55-65	65-75		2
	> 160	> 200		6
	40-54	50-64		6
	< 40	< 50		7
Diastolic Blood Pressure (mmHg)			> 110	6
Heart Rate (beats/min)	> 160	> 150		4
	< 90	< 80		4
Respiratory Rate (breaths/min)	61-90	51-70		1
	> 90	> 70		5
	apnea	apnea		5
PaO ₂ / FiO ₂ (mmHg) ^a			200-300	2
· · · · · ·			< 200	3
PaCO ₂ (mmHg)			51-65	
· · · · ·			> 65	
Glasgow Coma Score ^b			< 8	6
Pupillary Reactions			unequal or dilated	4
			fixed and dilated	10
PT/PTT			$1.5 \times \text{control}$	2
Total Bilirubin			> 3.5	6
Potassium (mEq/L)			3.0-3.5	1
			6.5-7.5	1
			< 3.0	5
			> 7.5	5
Calcium			7.0-8.0	2
			12.0-15.0	2
			< 7.0	6
			> 15.0	6
Glucose			40-60	4
			250-400	4
			< 40	8
			> 400	8
HCO ₃ (mEq/L) ^c			< 16	3
			> 32	3

Source: Pollack 1988

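### The PELOD renal item takes a creatinine measured on dialysis at face value, so dialysis started after Screening can count as a 10-point improvement or hide a worsening

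*Protocol*

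**What the plan says.** Section 10.4 fixes how the score is built: "The PELOD score is the sum of the 6 individual item scores (Appendix C"). In Appendix C the renal item has two levels. For this trial's ages (2 to 17 years) it is 10 points at creatinine of 100 µmol/L or more under 12 years, 10 points at 140 µmol/L or more from 12 years, and 0 otherwise. Dialysis is not an element of any item.

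Section 10.4 also fixes which value counts: "Scores should be calculated with the most recent values prior to the assessment time point". Its penalty rule is limited to absent data: "Missing values at Hour 24, due to death or treatment failure, will be assigned the worst possible score".

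Dialysis is foreseen and recorded. Section 8.2 covers "All medications and supportive therapies (including renal replacement therapy and ventilation support) that are administered from Screening through the Day 28 follow-up", and also lists "Concomitant procedures, such as dialysis, mechanical ventilation" among the procedures to be captured through Day 28. No exclusion criterion in Section 7.2 concerns it.

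Change in PELOD from Screening to 24 hours is a secondary endpoint (Section 5.4). Section 6.1 gives it a further reading: "The risk of mortality will be assessed using the PELOD score at Hour 24".

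**The concern.** Dialysis removes creatinine, so a value measured on dialysis does not show what the child's own kidneys are doing. Under the rules as written, a child whose kidneys have failed enough to need dialysis after dosing can lose the 10 renal points. A new need for organ support then enters the data as a fall in an organ-dysfunction score. Dialysis can also hold creatinine below the cut-off in a child who would otherwise have crossed it upward, and the score then shows no change.

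The trial has one arm, so no control group shares the same artefact. The renal item is also one a reader will look at closely. Section 4.5 reports significant effects of angiotensin II on renal blood flow in humans. Section 4.4 reports a marked fall in renal blood flow in septic sheep, although renal function improved there.

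Elsewhere the score does allow for treatment. The Glasgow value is to be non-sedated, pupils are not assessed after iatrogenic dilation, and ventilation is itself scored, with a note on what qualifies ("The use of mask ventilation is not considered to be mechanical ventilation"). Renal support has no such rule.

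**Working it through.** **Inputs**

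- Renal item R: 10 if creatinine is at or above the cut-off (100 µmol/L under 12 years, 140 µmol/L from 12 years), otherwise 0 (Appendix C).
- Item maxima in Appendix C: neurologic 20, cardiovascular 20, renal 10, respiratory 10, hematologic 10, hepatic 1. The total is 20+20+10+10+10+1 = 71.
- Value used: the latest measured before the time point (Section 10.4).
- n = 10 to 30 (Sections 6.4 and 12).
- Dialysis frequency: not given.

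**Renal contribution to the change score**, Hour 24 minus Screening, other items held constant. RRT = renal replacement therapy. The last column scores R = 10 whenever the child is on RRT at the time of the creatinine used.

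| Screening | Hour 24 | As written | On-RRT rule |
|---|---|---|---|
| no RRT, at/above cut-off | RRT, below | 0 − 10 = −10 | 10 − 10 = 0 |
| no RRT, below | RRT, below | 0 − 0 = 0 | 10 − 0 = +10 |
| no RRT, at/above | RRT, at/above | 10 − 10 = 0 | 10 − 10 = 0 |
| RRT, below | RRT, below | 0 − 0 = 0 | 10 − 10 = 0 |
| RRT, below | no RRT, at/above | 10 − 0 = +10 | 10 − 10 = 0 |
| RRT, below | no RRT, below | 0 − 0 = 0 | 0 − 10 = −10 |

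The first two rows flatter the treatment period. The last two run the other way. The middle two are neutral.

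**Does another rule catch the first row?** The worst-score rule does not, because it needs a missing value and a creatinine measured on dialysis is not missing. The protocol does not define treatment failure, but even if dialysis were read as such the value would still be present. Last observation carried forward also applies only to missing values.

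**How large a fall crosses the cut-off?** The starting values are assumptions chosen to show a range.

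- Under 12 years, to 99 µmol/L: from 100, 1.0%; from 150, 1 − 99/150 = 34.0%; from 200, 1 − 99/200 = 50.5%.
- From 12 years, to 139 µmol/L: from 140, 0.7%; from 210, 1 − 139/210 = 33.8%; from 280, 1 − 139/280 = 50.4%.

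**Effect on the mean.** With k children in the first row, the mean change moves by −10k/n.

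| n | k = 1 | k = 3 |
|---|---|---|
| 10 | −1.00 | −3.00 |
| 15 | −0.67 | −2.00 |
| 20 | −0.50 | −1.50 |
| 25 | −0.40 | −1.20 |
| 30 | −0.33 | −1.00 |

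**Net effect.** The two scorings differ only when a child is on RRT with creatinine below the cut-off. Let h be the number of such children at Hour 24 and s the number at Screening. The mean as written minus the mean under the on-RRT rule is 10(s − h)/n. It is zero when h = s, favourable to the drug when h > s, and unfavourable when s > h.

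**The case against.** The strongest reply is that PELOD is a published instrument, reproduced with its source and applied as published. On this view the complaint is about the instrument, and a sensitivity analysis belongs in the SAP, to which Section 12 defers. Part of this stands: the published scoring should remain the main analysis, and the quoted sentence contains no error or contradiction. But the protocol does not leave the scoring open. It fixes the sum, the value to use and the missing-data rules, and it makes allowance for sedation and iatrogenic pupil dilation. The gap therefore lies in a rule the protocol sets.

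A second reply is that other items are also measured under support: gas exchange on ventilation, systolic pressure on vasopressors. That is true, and PELOD reflects organ support only in part. Still, ventilation contributes at least a point, whereas dialysis contributes nothing and can remove 10.

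A third is that a crude correction brings its own distortion. Scoring 10 for any dialysis in the preceding 24 hours would penalise a child who came off dialysis soon after dosing and now has a normal creatinine. This is right, and it is why the rule should look only at the time of the creatinine used. Even then, a child dialysed without ever reaching the cut-off goes from 0 to 10, so the result must be labelled as a departure from the published score.

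A reader might also infer a definite bias, for example by taking 5% to 30% of children as affected and multiplying by 10 to get 0.5 to 3.0 points. The documents do not support that. The rate would have to be for a joint event: at or above the cut-off at Screening, dialysis started afterwards, and below the cut-off by Hour 24. The protocol does not give even a plain dialysis rate, and zero is possible.

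**Conclusion.** The point holds in a limited form. As fixed in Section 10.4 and Appendix C, dialysis started between the two scores can be recorded as a 10-point improvement or can mask a worsening. The size is certain only per child: 10 of 71 points, or 1.0 point of the mean change at n=10 and 0.33 at n=30. The per-child figure assumes that the cut-off is crossed and that the other items do not change. The total depends on h and s, which are unknown, so the net bias may be zero or may run against the drug.

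Three stronger readings should be resisted:

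- Not every child on dialysis gains: one who stays at or above the cut-off, or who was already below it on dialysis at Screening and remains so, shows no change.
- The protocol has no category of recovered organ function. That would be an interpretation of a falling score.
- The trial's success criterion is not in doubt. The primary endpoint and Table 10 rest on MAP and NED at Hour 2, and PELOD is a descriptive secondary endpoint on which no decision depends.

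The issue is whether that secondary result can be interpreted, and it is cheap to resolve before the data are seen.

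**What to change.** Keep the published PELOD scoring as the main analysis. Add one pre-specified sensitivity analysis in which the renal item is scored 10 when the child is receiving renal replacement therapy at the time of the creatinine value used. Apply it identically at Screening and Hour 24, with no blanket 24-hour look-back. Beside the PELOD result, report how many children were on dialysis at Screening and how many started before Hour 24.

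The cost is a sentence or two of analysis text, one derived variable, and a sensitivity result that departs from the published score and must be labelled so. Dialysis is already recorded under Sections 8.2 and 11.1.1. The sponsor should confirm that the CRF captures its start and stop times, because Section 8.2 spells out times for vasopressors but not for procedures.

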10.5. Tissue Oxygen Saturation

Tissue oxygen saturation will be measured non-invasively with near-infrared spectroscopy (NIRS), if available, and if feasible for the patient, at baseline, Hour 2, and Hour 24.

11. ASSESSMENT OF SAFETY

11.1. Safety Parameters

11.1.1. Medical History and Concomitant Medications

A full medical history will be taken during Screening and should include the patient's demographic information, surgical history, concurrent medical conditions, concomitant medications and procedures.

All medications and supportive therapies that are administered during administration of LJPC-501 and up to Day 28, including the indication, must be recorded on the appropriate CRF and in the source documents. For vasopressor medications only, start and stop date(s), dose, and amount administered, including dose adjustments, will also be recorded for vasopressors administered up to 2 days prior to, during LJPC-501 administration, and through Day 28. The total daily dose of administered vasopressors may be recorded after completion of LJPC-501 administration. Concomitant procedures, such as dialysis, mechanical ventilation, and any procedures used to diagnose or treat an SAE, will also be recorded though Day 28.

11.1.2. Physical Exam

A limited physical examination, focusing on extremities, abdominal region and neurological system, will be performed at Screening and at EOS. Body weight and height will be measured or documented at Screening only. Standard of care procedures performed prior to informed consent may be used to qualify patients for the study.

11.1.3. Vital Signs

Blood pressure, respiratory rate, and body temperature should be assessed at Screening, just prior to initiation of dosing on Day 1, on Day 1 at Hour 2, at Hour 24, once daily on Days 2 to 7, and at EOS.

11.1.4. ECG

Electrocardiogram assessments will be performed at Screening and at Hour 24 after initiation of LJPC-501, if possible.

